BAT and cardiovascular function. Recent studies have investigated the endocrine role of BAT to influence cardiovascular function. UCP1^{-/-} knockout mice had greater cell death, greater adverse remodeling, and worse survival in catecholamine-induced cardiomyopathy (38). These detrimental effects in UCP1^{-/-} knockout mice were prevented with transplantation of BAT from wild-type mice, suggesting that thermogenically active BAT has a cardioprotective effect. Additionally, BAT transplantation increases glucose uptake to the heart (36). Taken together, these studies indicated that BAT can influence heart function.

BAT as an endocrine organ. BAT functions as a secretory organ, releasing various secreted factors that act on other tissues and organs (2, 14, 36, 40). Several BAT-derived molecules, called “batokines” have been identified to function in an autocrine, paracrine, and endocrine manner (40). Previous studies have demonstrated that increasing the amount of BAT through a transplantation model improved whole-body metabolic health and increased insulin-stimulated glucose uptake in the heart and WAT (14, 36). Recent work has identified a batokine, the lipid 12,13-diHOME, to be increased in circulation in response to various stimuli in both rodents and humans and increases fatty acid uptake in BAT and skeletal muscle (25, 39). In line with a reduction in BAT, 12,13-diHOME is decreased in older adults in comparison to young counterparts (35). These studies suggest the inability of BAT to secrete batokines with aging may impair whole-body metabolism and cardiovascular function in older adults.

Study Objectives

Primary Objective

To define the role of BAT and 12,13-diHOME in the age-induced impairments in metabolism and cardiac function, and determine if increasing BAT mass or its endocrine function is a viable therapeutic strategy to improve metabolic and cardiovascular function in the elderly.

Study Design

Research Design

The proposed clinical study is a single site prospective, two group, controlled exercise training study of older athletes (OA) (n=15 completers) and older sedentary (OA) (n=15 completers) consisting of three distinct but connected phases:

Phase I: Pre-Intervention, Screening and Baseline testing

Phase II: Intervention, Exercise Training

Phase III: Post-Intervention, Follow-Up testing

A series of physiologic and clinical/health outcomes will be assessed before and after the exercise intervention period:

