1. Morning resting fasted variables: blood pressure; blood glucose and lipids
2. Physical Examination, Resting ECG, Urine collection
3. Cardiorespiratory fitness (VO₂peak) determined via a graded cycle ergometry test.
4. Physical function: The Short physical performance battery (SPPB) will be used to measure lower extremity performance as a secondary outcome.
5. Body composition by DEXA scan - bone mineral density, total and partitioned lean mass, estimated visceral fat.
6. Muscle strength and power: Quadriceps muscle performance testing (maximal strength and power) will be performed using a Biodex dynamometer.
7. Hyperinsulinemic euglycemic glucose clamp to assess whole body insulin sensitivity.
8. Echocardiograph measurements to assess cardiac function.
9. MR Imaging for BAT Mass

Participants in the OS group will enter a progressive 8-week supervised aerobic and resistance training program at the exercise training facility at the TRI. Blood will be collected before and after the intervention to assess circulating Batokines. A complete Schedule of Activities (SOA) can be found in the Appendix.

The expected duration for a participant in this study is approximately 120 days.

Males and females in the age ranges 65-90 years will be recruited from AdventHealth's electronic medical record (EMR), senior centers, television, radio and social media advertisements, mass mailing lists from the Orlando, FL catchment area, and by contacting potential participants on the AdventHealth TRI's participant database.

Study Site(s)/Location(s) and Number of Participants

AdventHealth Orlando site locations: Translational Research Institute, [name].

Estimated number of participants at AdventHealth Orlando site (including screenings): 36

Estimated number of participants at external sites: 0

Total number of all sites: 1

Estimated number of participants at all sites combined (including screenings): 36

Multi-Site Research Logistics/Communication Plan

N/A

Research Conducted in a Foreign Country

N/A

Community-Based Participatory Research

N/A

Participants Selection

Vulnerable Populations (if applicable)

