5. Participant has had a significant cardiovascular event (e.g. myocardial infarction, stroke) ≤ 6 months prior to screening visit; or stated history of congestive heart failure; or participant has evidence of cardiovascular disease assessed during the ECG at screening. In the event of a positive stress test, participants are referred to their primary care physician. If the electrocardiogram (ECG) is determined to be a false positive, participant may be allowed to participate in study after confirmatory records obtained.
6. Current infection (requiring prescription antimicrobial or antiviral medication, or hospitalization), or corticosteroid treatment (with the exception of inhaled or topical steroids) in the last 3 months prior to screening visit.
7. Participant is currently taking anti-inflammatory medication or has had anti-inflammatory medication within 1 week prior to screening (including over the counter formulations; e.g. Aleve, Motrin, ibuprofen, naproxen, low dose aspirin).
8. Surgery requiring >2 days of hospitalization in the last 3 weeks prior to screening visit.
9. Participant has an active malignancy (with the exception of basal cell) or autoimmune disease.
10. Participant has a chronic, contagious, infectious disease, such as active tuberculosis, Hepatitis B or C, or HIV, per self-report.
11. Participant is an amputee and/or has presence of partial or full artificial limb.
12. Participant currently has uncontrolled severe diarrhea, nausea or vomiting.
13. Participant has uncontrolled severe (including stage III or above) gastrointestinal absorption-related disorders, within 3 months of screening, such as: obstruction of the gastrointestinal tract, inflammatory bowel disease, short bowel syndrome, gastroesophageal reflux disease, gastroparesis, peptic ulcer disease, celiac disease, intestinal dysmotility, diverticulitis, ischemic colitis and bariatric surgery.
14. Cannot abstain from alcohol for the duration of the testing periods.
15. Subjects who fulfill any of the contraindications for MRI; examples include metal implants, devices, paramagnetic objects contained within the body and excessive or metal-containing tattoos.
16. Unable to participate in MR or DEXA assessments due to physical limitations of equipment tolerances (e.g., MRI bore size and DEXA 450-pound weight limit), claustrophobia, or based on Investigator's judgment at screening.

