17. Participant cannot refrain from taking medications/dietary supplements/herbals or substances that could modulate glucose metabolism, or are considered anabolic, or reduce weight (fat mass) in the opinion of the PI or Physician, starting two weeks prior to enrollment and over the entire course of the study. These include progestational agents,

steroids, growth hormone, dronabinol, marijuana, calcium-betahydroxy-betamethylbutyrate (CaHMB), free amino acid supplements and dietary supplements to aid weight loss.

18. Participant has hypothyroidism (TSH \geq 10 mIU/L) or hyperthyroidism (TSH $<$ 0.4 mIU/L).
19. Presence of any condition that, in the opinion of the Investigator, compromises participant safety or data integrity or the participant's ability to complete the study.
20. Because all women participating in this project will be post-menopausal, there will be no need for a pregnancy test prior to DEXA procedures. Females currently on hormone replacement therapy (HRT) can participate in the study if they have been on a stable dose of HRT for at least 6 months and will continue to be on HRT during the study.
21. Potential participants taking stable doses of medications for the last 30 days prior to screening for Blood pressure, cholesterol, GERD may be permitted to participate.
22. Participant becomes Covid-19 positive at any point during the study.

Resources Available

We attest that all AdventHealth Translational Research Institute faculty and staff will be trained, and this training will be documented as described in AdventHealth Translational Research Institute Work Instruction 031.100.015 Documentation of Protocol Training.

We will implement regular, ongoing discussions between the PI and coordinator as per the AdventHealth Translational Research Institute SOP 030.000.002 Oversight of Research Studies at the Translational Research Institute. The coordinator will review source and communicate with all applicable study team members involved in the study on a regular basis regarding reportable new information, implementing amendments, study progress, and quality assurance/control.

The AdventHealth Translational Research Institute facilities are state of the art and we have within our building all required resources and staff to execute the study. We have a medical oversight team, Medical Oversight Committee, as well as a Quality Committee to appropriately monitor and address adverse events.

Study Procedures

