Waiver of Written Documentation of Consent or Waiver of Consent

N/A

Randomization

N/A

Study Visits

All study visits will be conducted at the AdventHealth Translational Research Institute.

PHASE I – SCREENING AND PRE-INTERVENTION TESTING

Both older athlete and older sedentary groups will undergo the screening and pre-intervention testing phase. See “Appendix: Schedule of Activities” for a table description of the procedures that will be performed during PHASE I.

Screening: SV1

Approximate visit time: ~ 3 1/2 hours

Volunteers will arrive, after an 8 hour overnight fast, to the AdventHealth TRI. Following voluntary written informed consent, all research participants will undergo a screening process for eligibility. This process may be repeated if necessary, under the discretion of the Medical PI. The following listed below procedures will be performed:

Demographics, Medication & Medical History, Physical Examination, Vital Signs, and Anthropometrics will be obtained. A full physical examination will be performed by a study physician, physician assistant, or nurse practitioner and will include general assessment of the following: head, ears, nose, eyes, throat, heart, lungs, abdomen, extremities, skin, neurological functioning, and any other impressions or problems noted by the provider at the time of exam. This will also include height, weight (metabolic), BMI, blood pressures, heart rate, respirations, temperature, medication, supplement history and a basic assessment of cognitive functioning via the Mini Mental State Examination (MMSE).

Electrocardiogram (ECG). A standard 12-lead ECG will be performed. Electrodes will be placed on the chest to provide a tracing of the electrical activity of the heart.

Physical activity questionnaires will be administered at screening. The Exercise History and Physical Activity Scale for the Elderly (PASE) are instruments that measures the level of habitual physical activity for individuals. The CHAMPS Physical activity health questionnaires will also be administered at screening. The MMSE will be administered at this time too.

Fasting blood draw to measure: a lipid panel; Complete Metabolic Panel (CMP); Complete blood count with differential (CBC w/ diff); TSH and HbA1c. Total blood volume for screen labs 14mls. Safety labs may be repeated per Investigator discretion, if needed. Blood draws may also take place at visit 2 or visit 3.

Urine collection for urinalysis.

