Waist Circumference Measurements which are a surrogate measure of abdominal fat will be conducted during screening. The Gulick II tape measure will be used for accuracy in obtaining duplicate waist measurements. All circumferences will be measured in centimeters directly on the skin.

Hand-Grip Strength Test. All participants will perform a hand grip test that will be conducted three times with 1 minute of rest between each repetition using the dominant hand of each participant. The greatest grip strength and the average of the three tests will be recorded.

Lower extremity performance battery. The Short Physical Performance Battery (SPPB) is a brief performance-based test that will be used to measure lower extremity performance. The SPPB consists of three tasks: five repeated timed chair stands, timed standing balance (with feet in parallel, semi-tandem, and tandem positions), and a 4-meter walk to determine usual gait speed.

Step Test: Each participant will be asked to complete a timed step test.

Covid Testing: Participant must have a negative covid test 1 week prior to the next visit. Covid testing may take place on a separate visit when SV1 is not within 1 week of V1.

Screening tests may be repeated if the Investigator deems necessary.

Visit 1

Approximate visit time: ~ 3 hours

Review of Adverse Events, Concomitant Medications

Vital Signs

Body Weight

3-Day Food Diary: Participants will be given a food diary and asked to record what foods and drinks they eat over a 3-day period. Participants will return the completed diary on visit 2.

Fasting blood draw to collect EDTA plasma. Circulating lipids related to BAT activity and mass will be measured in plasma samples. Total blood volume will be 10 mls. Safety labs may be repeated per Investigator discretion, if needed.

MR Imaging for BAT Mass. Brown adipose tissue will be differentiated from white adipose tissue using fat fraction and T2* relaxation time maps generated from a commercially available modified 6-point Dixon (mDixon) water-fat separation method. MRI scans will be performed on a Philips 3T using axial, coronal, and sagittal slice orientations to provide anatomical reference scans in the neck and body area. Quantitative mDixon scans will be used for calculating proton density fat fraction (PDFF) maps. The participant may be removed from the magnet and repositioned during the exam in order to determine the same day variability of this method.

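### Item 21 requires stable blood-pressure and cholesterol drugs only up to screening, so a dose change between the OS tests could be read as a training effect

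*Combined protocol and SAP*

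**What the plan says.** Exclusion Criteria, item 21, is worded as a permission. People "taking stable doses of medications for the last 30 days prior to screening for Blood pressure, cholesterol, GERD" may take part. It names no time point after screening, and the Schedule of Activities marks the eligibility check only at SV1. Item 7 is anchored to screening in the same way; its exclusion reads "Participant is currently taking anti-inflammatory medication or has had anti-inflammatory medication within 1 week prior to screening".

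Other items in the same list do set on-study conditions. Item 14 excludes anyone who "Cannot abstain from alcohol for the duration of the testing periods". Item 17 bars glucose-modulating, anabolic and weight-reducing substances "starting two weeks prior to enrollment and over the entire course of the study". Item 20 requires hormone replacement to have been stable for at least six months and to continue while the person is in the study.

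The Research Design section states that "physiologic and clinical/health outcomes will be assessed before and after the exercise intervention period". First on its list is "Morning resting fasted variables: blood pressure; blood glucose and lipids". The SV1 procedures include "Fasting blood draw to measure: a lipid panel", and the schedule shows this panel again in Phase III. Visits also include a "Review of Adverse Events, Concomitant Medications", but no action or analysis is tied to it.

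The Phase III text assigns post-intervention testing to the OS group. The Statistical Analysis Plan applies repeated measures ANOVA to the dependent variables in OS. It names neither blood pressure nor lipids, and it has no medication term, exclusion or sensitivity analysis.

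**The concern.** Item 21's drugs are defined by what they treat: blood pressure and cholesterol. The same two quantities are listed as before-and-after outcomes. The rule secures stable dosing up to screening, but the comparison needs it between the two tests.

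OS is compared with itself and no untrained group is retested, so nothing in the design absorbs a drug change made during the interval. If an antihypertensive is started, or a statin dose raised, between baseline and post-test, the resulting fall enters the OS mean change and could be credited to training. A drug stopped or reduced could hide a real training effect. At stake is the reading of two secondary outcomes.

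**Working it through.** **1. Rules side by side**

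| Item | Drugs | Condition before the study | Condition on study |
|---|---|---|---|
| 17 | Glucose-modulating, anabolic, weight-reducing | From two weeks before enrollment | Yes, whole study |
| 20 | Hormone replacement | Stable for at least 6 months | Yes, to continue |
| 21 | Blood pressure, cholesterol, GERD | Stable for 30 days before screening | None stated |

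Of the three quantities in the first listed outcome, glucose is covered on study by item 17. Blood pressure and lipids are not covered by item 21.

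**2. Interval not covered.** The inputs are nominal days from the Schedule of Activities: SV1 at D-54, V3 ending at D-6, V36 at D56, V39 at D71.

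- The item 21 look-back runs from D-54 - 30 = D-84 to D-54.
- Lipid panel from SV1 to its repeat (apparently V36; the table is damaged): 56 - (-54) = 110 days. The SV1 baseline is covered by the look-back and the interval after it is not. The SV1 section also lets blood draws fall at visit 2 or 3, so 110 days is not fixed.
- Blood pressure is taken at several Phase I and Phase III visits, and the plan does not say which reading is the baseline. The shortest interval is 56 - (-6) = 62 days. The longest is 71 - (-54) = 125 days.
- The permitted exercise extension of up to three weeks could lengthen these intervals.

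On any of these choices, none of the interval between the two readings falls inside the look-back.

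**3. Size.** The documents give no rate of drug change, no drug effect and no SD, so the shift can only be illustrated. If k of 15 OS completers change a drug and each change moves the outcome by d in the same direction, the OS mean change moves by k × d / 15. Both k and d are assumptions.

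| | k = 0 | k = 1 | k = 3 |
|---|---|---|---|
| LDL, d = 10 mg/dl | 0 | 10/15 = 0.7 | 30/15 = 2.0 |
| LDL, d = 40 mg/dl | 0 | 40/15 = 2.7 | 120/15 = 8.0 |
| Blood pressure, d = 5 mmHg | 0 | 5/15 = 0.3 | 15/15 = 1.0 |
| Blood pressure, d = 15 mmHg | 0 | 15/15 = 1.0 | 45/15 = 3.0 |

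One start and one stop of equal effect give (d - d)/15 = 0.

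**4. Precision of an analysis without changers.** The half-width of the 95% interval for a mean paired change is t(0.975, n-1)/√n, in SDs of the change:

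- n = 15: 2.145/3.873 = 0.55
- n = 14: 2.160/3.742 = 0.58
- n = 12: 2.201/3.464 = 0.64

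**5. Reach of a wording change.** The current version is dated August 2023 (read as 11 August) and funding ends 31 January 2024, which is 173 days. SV1 to V39 takes 125 days. A new OS participant would have to be screened within 173 - 125 = 48 days, by about 28 September 2023.

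**The case against.** The best opposing case has five parts.

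- **Eligibility narrows the risk.** Exclusion 3 removes untreated or poorly controlled hypertension (above 150 systolic, 95 diastolic). Inclusion 6 limits LDL to 150 mg/dl and requires triglycerides below 350 mg/dl. With 30 days of stable dosing as well, the people most likely to need a new or changed prescription are largely screened out. This stands. It lowers the likely number of changes but does not make it zero.
- **Medication is already reviewed at visits, and item 19 allows exclusion for data integrity.** This stands as to recording. But item 19 is a general discretion clause, and no analytic use of the record is stated.
- **The outcomes are minor.** The SAP does not name blood pressure or lipids. They count as secondary only through the general reference to phenotype data in the endpoints section. This stands, and it keeps the point small.
- **The fix prevents little.** A clinical-need exemption will cover most real changes, and few participants remain to be enrolled. This stands for the wording change but not for the table and supportive analysis.
- **The missing control is the larger problem.** OS change has many possible causes besides training. This stands; the present change does not cure it.

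A reader might also infer that anti-inflammatory use biases the BAT and 12,13-diHOME results, because item 7 looks back only from screening too. The documents do not support that. They state no effect of these drugs on either measure and no purpose for item 7.

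**Conclusion.** The point holds for item 21, as an inexpensive improvement. The stability rule covers none of the interval over which OS blood pressure and lipids are compared, and under the SAP as written a drug change in that interval could be read as a training effect.

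Its size is unknown. The illustrated shifts of 0 to 8.0 mg/dl LDL and 0 to 3.0 mmHg rest on assumed numbers of changers and assumed drug effects, all acting in one direction. With no SD in the documents, they cannot be judged against the variability of the outcomes. A reader might take them as an estimate of bias, or conclude that a misreading will occur. Neither follows: no change may happen, changes may offset, and the visit records would allow an alert analyst to notice one. Nor is medication uncontrolled after screening, since item 17 and the visit reviews apply throughout. No bias in BAT or 12,13-diHOME is claimed.

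The conclusion rests on OS alone being retested. The Phase III text and the payment table, which ends the athlete group at V3, agree on this. The schedule's OA row is hard to read in the extracted table, but a retest of trained athletes would not supply an untrained control either.

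**What to change.** 1. **Protocol, item 21.** Add that these drugs are to stay at a stable dose from screening through the last post-test unless a change is clinically needed, and that the date and reason of any change are recorded.
2. **SAP.** Keep the full-set OS analysis as the main one. From the existing medication record, tabulate OS participants with any item 21 drug started, stopped or re-dosed between baseline and post-test. State which blood-pressure and lipid readings serve as baseline. As a supportive analysis, repeat the OS pre-post comparison for blood pressure and lipids without those participants, and compare estimates and intervals rather than p-values. Specify this before results are seen.

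**Cost.** One sentence in the protocol, one count table, and one supportive analysis of data already collected. The sample size does not change.

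**Downsides.** There are fewer pairs: with three changers removed, the interval half-width grows from 0.55 to 0.64 SD. The exclusion also conditions on post-baseline behaviour, because training may itself lead to a dose change, so the analysis can only be supportive. The wording change reaches few remaining participants, but the table and analysis cover everyone already tested.

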Increasing age is directly correlated to greater prevalence of both metabolic and cardiovascular disease (6). Aging results in impaired glucose metabolism and increased insulin resistance; a third of the population over 60 years of age has diabetes (elderly-onset diabetes), and an additional third of this population presents with prediabetes (18). There is also a higher prevalence of cardiovascular mortality in older adults with impaired glucose metabolism compared to those with normal glucose tolerance. An important tissue that combats metabolic disease and is cardioprotective is brown adipose tissue (BAT) (3, 8, 31, 36, 39). BAT is a thermogenic tissue that contains large amounts of mitochondria to dissipate chemical energy as heat. When activated, either by cold-stimulation or increasing the amount of BAT by transplantation, BAT increases energy expenditure, decreases plasma glucose and lipids, and improves systemic metabolism. Previous work have demonstrated that increasing the amount of BAT by transplantation improves metabolic health and has an endocrine effect on the heart (14, 36, 38). Additionally, studies have identified that cold-activation or exercise releases from BAT a “batokine”, the lipid 12,13-diHOME, which has a robust effect on metabolism (25, 35)

BAT has great potential as a therapeutic target to combat both metabolic and cardiovascular disease, but BAT mass decreases with age (8, 12, 30-32, 39). The objective of this study is to define the effect of aging on BAT mass in a cohort of older sedentary adults and older athlete adults. A secondary objective is to define how changes in BAT mass with aging relate to changes in BAT derived lipokines (12,13 diHOME). Finally, we would like to further validate the method for determining BAT mass using MRI.

This work embodies a multidisciplinary and multi-Investigator approach and is the product of an ongoing successful collaboration between experts in magnetic resonance imaging, BAT, and aging at AdventHealth Translational Research Institute (TRI), Orlando, FL.

The proposed study is a prospective, two group, controlled exercise training study consisting of three distinct but connected phases:

- I) Screening Phase and Pre-Intervention testing,
- II) Exercise Training Intervention Phase, and
- III) Post-Intervention testing.

Eligible participants will be assigned to one of two groups:

1. Older adults who are regularly engaged in endurance exercise (OA-Older Athlete)
and

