Biospecimen samples will be stored in ultralow temperature freezers and liquid nitrogen dewars or other storage units located at the AdventHealth TRI Laboratory Room 2404. The AdventHealth TRI facility is secured via key card and equipped with a back-up generator system. Laboratory personnel in the facility have 24/7 key-controlled access to the laboratory. Chain of custody of biospecimen samples is maintained through requisition forms and in the StarLIMS database. Specimen tubes are coded, and specimen requests and distribution are documented.

The plasma/serum samples will be stored indefinitely, or until a sample is fully used. All biological specimens will be stored without identifiers or linkage codes.

After study aims have been achieved and study related endpoints have been measured and analyzed, any remaining biospecimens will be stored at the AdventHealth TRI Laboratory Room 2404 and will then be considered as “archived biospecimens.” Archived biospecimens will be used for any additional hypothesis-related experimentation or testing for the **purposes of this study, consistent with the original aims**, which cannot be predicted at the time the protocol is developed due to the evolving nature of scientific exploration.

Additionally, archived biospecimen samples may be stored indefinitely for future research. Archived biospecimens could be used for **separate research** by **both** AdventHealth Orlando scientists and scientists outside of AdventHealth TRI. This would be allowed for **research of any type** (without limitation to disease, process, or research methods) if it has scientific merit as determined by the Principal Investigator, with an additional review by the respective Program Director. For research outside of AdventHealth Orlando, a Material Transfer Agreement will be obtained, which will govern the transfer and chain of custody of the biospecimens outside of AdventHealth Orlando.

Study Outcome Measures (Endpoints)

The major outcomes of the study are collection of imaging of BAT by magnetic resonance imaging and circulating lipokines (12,13-diHOME) from 15 participants in each of the older athlete and sedentary groups. In addition, collection of all phenotype data are considered secondary outcome measures, including: Aerobic fitness (VO₂max test, DEXA, Muscle power and strength, Physical function (SPPB), and accelerometry data).

Data Management and Quality Plan

Data De-identification

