The primary purpose of this protocol is to understand the role of physical activity on BAT mass and circulating batokines, and how these variables relate to cardiac and physical function in older adults. A formal sample size calculation was not performed. Rather, we referred to published studies with similar experimental designs (determination of BAT mass by PET scan) as a guide for sample size determination. From the published literature we determine that an n=15 per group (active and sedentary) will provide sufficient statistical power to detect differences in BAT mass.

Statistical Analysis Plan

The analysis will involve multiple steps and draw on statistical methods ranging from simple descriptive statistics to the modeling of repeated measures outcome data accounting for potential missing observations. The major outcomes of the study, the BAT mass, circulating batokines, muscle mass, strength, power and quality, and VO₂max will be compared using an unpaired student t-test to explore baseline differences between older athletes and older sedentary groups. Additionally, repeated measures ANOVA will be performed on the dependent variables as a function of the exercise intervention in the older sedentary group. Multiple linear regression will be used to determine how BAT mass and circulating batokines explain variation in physical characteristics of muscle (strength, quality) and cardiovascular health (VO₂max). Sex will be explored as a biological variable.

Potential Risks and Benefits

Potential Benefits

Participants will likely receive no direct benefit from taking part in this research study.

Potential Risks

RMR/RQ. There is no physical risk associated with RMR/RQ. Other risks include a feeling of claustrophobia experienced by some participants while under the transparent “hood”.

Protection Against Risk:

- A member of the study staff will remain with the subject at all times to ensure his/her comfort.

Blood draws and Intravenous lines (lab samples and infusions, e.g.). There is a risk of pain, vasovagal syncope, hematomas, and/or infection at the blood draw site (low risk of serious AEs). The total volume of blood drawn is over the course of the study is approximately 372 mls.

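### The plan does not mask BAT image analysis to group or visit, or fix the PDFF and T2* cut-offs and region rule, which mainly exposes the OS before-and-after contrast

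*Combined protocol and SAP*

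**What the plan says.** The only account of the BAT measurement is the MR imaging paragraph under Visit 1: "Brown adipose tissue will be differentiated from white adipose tissue using fat fraction" together with T2* maps, obtained from a 6-point mDixon sequence at 3T. It adds that "Quantitative mDixon scans will be used for calculating proton density fat fraction (PDFF) maps". No PDFF or T2* range, depot or region, segmentation method, software or analyst is named. A repeat scan is optional: "The participant may be removed from the magnet and repositioned during the exam in order to determine the same day variability". The Introduction lists further work on the method itself as an aim: "we would like to further validate the method for determining BAT mass using MRI".

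The outcome ranks high. Study Outcome Measures states "The major outcomes of the study are collection of imaging of BAT by magnetic resonance imaging and circulating lipokines". The Statistical Analysis Plan puts BAT mass first in a longer list of major outcomes, and Sample Size Determination ties n = 15 per group to it.

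Two BAT contrasts are planned. At baseline the outcomes "will be compared using an unpaired student t-test to explore baseline differences between older athletes and older sedentary groups". Within OS, a repeated measures ANOVA examines change with training. Randomization is marked not applicable. The Phase III section limits post-intervention testing to OS.

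**The concern.** Fat fraction and T2* are quantitative maps, but turning them into a BAT mass requires two choices: which region to include and which voxel values count as BAT. If those choices are open and the person making them can tell which scans are post-training, a small systematic shift between pre and post readings enters the OS contrast as an apparent training effect. The primary objective asks whether raising BAT mass is a viable strategy, so the hoped-for direction is clear there.

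The baseline OA-OS comparison has a weaker version of the same gap: group could be known to the analyst from other sources, and nothing prevents it. Separately, a cut-off chosen after looking at results adds a selection step that the reported p-value does not reflect. None of this can be repaired by analysis once unmasked values are the only ones available.

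**Working it through.** **1. Search for a safeguard.** The nearest provisions, and what each covers:

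- Data De-identification: device data carry a participant code (PID). This protects privacy; nothing says that group, visit or scan date is hidden from the image analyst. One participant keeps one code, so it links an OS baseline scan to its post-training scan.
- Data Quality: critical endpoints, as chosen by the investigators, receive quality-control analyses. No masked or duplicate MRI reading is described.
- Visit 1 repositioning: optional, and about same-day scan variability, not about analyst knowledge or choice of cut-off.
- The study-specific procedure document cited under the VO2max test is cited for monitoring of that test, not for imaging.

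None masks group or visit, and none fixes a cut-off or region.

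**2. What a label reveals.** Both groups have the MRI at Visit 1, so that label is the same for OA and OS. Phase III testing is for OS only, and the stipend table likewise ends at V3 for athletes. A Phase III label or date therefore identifies both OS and post-training. A baseline OS scan is exposed only when its PID ties it to a later scan. In the Schedule of Activities the OA row appears marked through Phase III but also shows end of study at V3; this may be a table-reading artefact and is not relied on.

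**3. Size, as an illustration.** The plan states no alpha, BAT standard deviation, effect size or reading error, and says that no formal sample size calculation was done, so it has no figure on this point to reproduce. From the plan: n = 15 per group, and 15 OS completers for the pre-post contrast. Assumed: two-sided 5%, no true effect, and a systematic shift of b standard deviations.

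The false-positive rate is P(|T| > t_crit), with T following a noncentral t distribution with noncentrality δ.

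- OS pre-post, b in SD of change (with two time points the repeated measures ANOVA equals a paired t-test): δ = b√15, 14 df, t_crit = 2.145.
  - b = 0.2: δ = 0.775, rate 0.112
  - b = 0.3: δ = 1.162, rate 0.192
- OA-OS at baseline, b in between-person SD: δ = b√(15/2), 28 df, t_crit = 2.048.
  - b = 0.2: δ = 0.548, rate 0.083
  - b = 0.3: δ = 0.822, rate 0.125

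The two values of b are in different units. With equal SDs at both times, SD of change = SD × √(2(1 − r)), where r is the pre-post correlation. The units coincide only at r = 0.5, so the two sets of rates should not be compared as if the same absolute shift lay behind them.

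**4. Cut-off selection.** A simulation of 20,000 null trials took the smallest of three two-sample p-values, one per candidate cut-off. The false-positive rate was about 13%, 10%, 8% or 7% when the resulting BAT values correlated 0.5, 0.8, 0.9 or 0.95. This applies only if the cut-off is selected on the results.

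**The case against.** Several points on the other side are sound and limit the claim.

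- A reader might infer that visit labels unmask the OA-OS comparison too. They do not: that test uses baseline values, and both groups share the same Visit 1 scan. What stands is that nothing keeps group information from the analyst by other routes.
- A reader might infer drift toward an expected result in both contrasts. The documents state no direction for OA against OS, and the title of one cited study points to low BAT activity in endurance-trained men. An expected direction is a reasonable inference only for OS pre-post.
- Manual contouring is not described, and segmentation could be automated. That would narrow the room for discretion, but regions, cut-offs and exclusions would still have to be set, and the plan does not say how.
- One cut-off applied to every scan does not by itself favour a group or visit. It inflates error only if picked on results.
- BAT shares top rank with 12,13-diHOME, and the baseline t-tests are described as exploratory. Even so, BAT is named first in both lists and the sample size is tied to it.
- The protocol leaves detail to separate procedures elsewhere, so an imaging procedure may exist. The supportable statement is that masking and cut-offs are not specified in this protocol and SAP.

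**Conclusion.** The concern holds as an unaddressed route to bias. The plan specifies neither masking of BAT image analysis nor a PDFF, T2* or region rule, for a first-named major outcome measured by a method that the study itself is still validating. It bears mainly on the OS pre-post contrast and more weakly on OA against OS at baseline.

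The rates of about 11% to 19% and about 8% to 13% rest on an assumed 5% two-sided level and assumed shifts of 0.2 to 0.3 SD that nothing in the documents anchors. They show sensitivity at n = 15; they are not estimates of what happened. A reader might infer that readings were in fact biased, and the documents give no evidence of that.

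Unstated cut-offs alone would be missing detail. Combined with unmasked reading in an open, non-randomised study, and given how cheap the remedy is, the change should be made.

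**What to change.** - Have data management release images to whoever performs the BAT segmentation under random codes, with group, visit, date and PID removed, and with OA, OS-pre and OS-post scans mixed in random order.
- Fix and date the PDFF and T2* cut-offs and the region rule before these masked reads, or cite the existing dated imaging procedure if there is one.
- Unmask only after the BAT values are locked, and report any other cut-offs as sensitivity analyses.
- If some scans have already been read unmasked, re-read the stored images under codes and disclose it. Enrolment was expected from September 2019 and this version dates from August 2023, so this is possible; the documents do not say whether reading has begun.

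The cost is a coding step for data management and reading in batches, so BAT values come later than with scan-by-scan reading. No extra scan, visit or reader is needed, and no number in the plan changes.
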